### **Anti-Tumor Effect Definitions**

Evaluable for objective response. Only those participants who have measurable disease present at baseline (obtained within 14 days of cycle 1, day 1) scan and have received at least one dose of therapy will be considered evaluable for response. These participants will have their response classified according to the definitions stated below. (Note: Participants who exhibit objective disease progression or die prior to the end of cycle 1 will also be considered evaluable.)

Measurable disease. Bi-dimensionally, contrast-enhancing, measurable lesions with clearly defined margins by CT or MRI scan, with a minimal diameter of 1 cm, and visible on 2 axial slices which are at least 5 mm apart with 0 mm skip. Measurement of tumor around a cyst or surgical cavity, if necessary, requires a minimum thickness of 3 mm. If there are too many measurable lesions to measure at each evaluation, the investigator must choose the largest two to be followed before a participant is entered on study. The remaining lesions will be considered non-measurable for the purpose of objective response determination. Unless progression is observed, objective response can only be determined when all measurable and non-measurable lesions are assessed.

Non-measurable evaluable disease. Unidimensionally measurable lesions, masses with margins not clearly defined, lesions with maximal diameter < 1cm.

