### **Response/Progression Categories**

Complete response (CR). All of the following criteria must be met:

1. Complete disappearance of all enhancing measurable and non-measurable disease sustained for at least 4 weeks. In the absence of a confirming scan 4 weeks later, this scan will be considered only stable disease.
2. No new lesions\*.
3. All measurable and non-measurable lesions must be assessed using the same techniques as baseline.
4. Participants must be on no steroids or must not be on increased doses of steroids within 2 weeks of assessment relative to the dose taken at the time of the previous assessment
5. Stable or improved non-enhancing (T2/FLAIR) lesions
6. Stable or improved clinically, for clinical signs and symptoms present at baseline and recorded to be disease related

*Participants with non-measurable disease cannot have a complete response. The best response possible is stable disease.*

*\*See immunotherapy considerations below regarding new lesions*

Partial response (PR). All of the following criteria must be met:

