#### CONFIDENTIAL

1. Greater than or equal to 50% decrease compared to baseline in the sum of products of perpendicular diameters of all measurable enhancing lesions sustained for at least 4 weeks. In the absence of a confirming scan 4 weeks later, this scan will be considered only stable disease.
2. No progression of non-measurable disease.
3. No new lesions.\*
4. All measurable and non-measurable lesions must be assessed using the same techniques as baseline.
5. Participants must be on no steroids or must not be on increased doses of steroids within 2 weeks of assessment relative to the dose taken at the time of the previous assessment
6. Stable or improved non-enhancing (T2/FLAIR) lesions on same or lower dose of corticosteroids compared to baseline scan.
7. Stable or improved, for clinical signs and symptoms present at baseline and recorded to be disease related clinically.

*Participants with non-measurable disease cannot have a partial response. The best response possible is stable disease.*

*\*See immunotherapy considerations below regarding new lesions*

Progressive disease (PD). Any of the following criterion must be met:

1. 25% increase in sum of the products of perpendicular diameters of enhancing lesions (over best response or baseline if no decrease) on stable or increasing doses of corticosteroids
2. Patients who decrease corticosteroid use within 2 weeks of MRI assessment relative to the dose taken at the time of the previous assessment cannot be classified as having progressive disease and should be classified as non-evaluable.
3. Any new enhancing measurable lesion\*
4. Clear clinical deterioration not attributable to other causes apart from the tumor (e.g. seizures, medication side effects, complications of therapy, cerebrovascular events, infection, etc.). The definition of clinical deterioration is left to the discretion of the investigator but it is recommended that a decline in the Karnofsky Performance Score (KPS) from 100 or 90 to 70 or less, a decline in KPS of at least 20 from 80 or less, or a decline in KPS from any baseline to 50 or less, for at least 7 days, be considered neurologic deterioration, unless attributable to co-morbid events or changes in corticosteroid dose.
5. Failure to return for evaluation due to death or deteriorating condition

*\*See immunotherapy considerations below regarding new lesions*

Stable disease (SD). All of the following criteria must be met:

1. Does not qualify for CR, PR, or progression.

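### Attachment 3 contradicts itself on whether a patient with both measurable and non-measurable lesions can be scored a complete or partial response

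*Combined protocol and SAP*

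**What the plan says.** Attachment 3 (Section 15.3) sets the response categories for the study.

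- Note under complete response: "Participants with non-measurable disease cannot have a complete response. The best response possible is stable disease".
- Note under partial response: "Participants with non-measurable disease cannot have a partial response. The best response possible is stable disease".
- Non-measurable disease, under the anti-tumor effect definitions, includes lesions under 1 cm in maximal diameter and masses without clear margins.
- A second route into that category is conditional: "If there are too many measurable lesions to measure at each evaluation, the investigator must choose the largest two to be followed". It continues: "The remaining lesions will be considered non-measurable for the purpose of objective response determination".

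Other sentences in the same attachment describe responders who have both kinds of lesion.

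- CR item 1 requires: "Complete disappearance of all enhancing measurable and non-measurable disease sustained for at least 4 weeks".
- PR item 1 requires: "Greater than or equal to 50% decrease compared to baseline in the sum of products of perpendicular diameters of all measurable enhancing lesions".
- PR item 2 requires: "No progression of non-measurable disease".
- The definitions add that, absent progression, "objective response can only be determined when all measurable and non-measurable lesions are assessed".
- The summary table of iRANO criteria at the end of the attachment contains no bar on response for non-measurable disease.

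Response rate and median duration of response are secondary endpoints (Section 3.3). Section 7.2.2 plans an exact 95% confidence interval for the response rate.

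**The concern.** The two notes lack the word 'only'. Taken at face value, they cap at stable disease anyone who has a non-measurable lesion, whatever happens to the measurable ones. The numbered criteria directly above them assume the opposite, so a reader must choose which text governs.

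The choice matters because a capped patient with measurable disease stays in the response denominator but cannot enter the numerator, and contributes nothing to duration of response. Any error from applying the notes therefore runs one way, toward a lower response rate.

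Inconsistent application is a realistic risk. The Study Summary lists four sites. Section 6.6 and footnote 22 of the Schedule of Events describe local reading by the investigator, and no central radiology review is described. Eligibility does not exclude multifocal disease as such, and inclusion criterion 11a admits some patients because of new tumor outside earlier radiation fields.

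**Working it through.** The plan states no figure for this point, so the main check sets the texts side by side.

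**Step 1. Score the same patient under each text.**

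| Illustrative patient | Numbered criteria | Notes as written |
|---|---|---|
| One measurable lesion shrinks 80%; a 6 mm satellite is stable | PR items 1 and 2 are met, so PR if the other items hold | Stable disease |
| Lesions too many to measure, two followed, the rest relabelled; all disappear for at least 4 weeks | CR item 1 is met, so CR if the other items hold | Stable disease |
| Two measurable lesions and nothing else; both disappear for at least 4 weeks | CR item 1 is met | No bar applies; CR if the other items hold |

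The first patient needs no relabelling, because a 6 mm lesion is already non-measurable by definition. The second depends on the investigator judging that there are too many lesions to measure, and no threshold is given for that. A patient with three lesions that can all be measured has none relabelled.

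**Step 2. Which endpoints depend on the choice.** Response rate and duration of response do. PFS6 depends on progression, death and remaining on treatment (Section 7.1.3), not on whether a non-progressing patient is labelled CR, PR or SD. As a side check, an exact binomial calculation for the Simon design (stop at 7 or fewer of 18, success at 23 or more of 43, 0.40 versus 0.60) gives alpha 0.0474 and power 0.8272. These match the stated 0.047 and 82.7%, and neither uses response category.

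**Step 3. Size, for illustration only.** Inputs:

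- N = 43, the planned phase II enrolment (Section 7.1.3), used here as the denominator.
- p = true response rate. Not given in the documents; assumed 20%.
- f = share of true responders who also have a non-measurable lesion. Not given; assumed 10-30%.
- Every reader is assumed to apply the notes as written.

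Scored rate = p × (1 − f). Responders lost = N × p × f. Expected true responders = 43 × 0.20 = 8.6.

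- f = 10%: scored rate 0.20 × 0.9 = 18%; lost 8.6 × 0.1 = 0.86.
- f = 20%: scored rate 0.20 × 0.8 = 16%; lost 8.6 × 0.2 = 1.72.
- f = 30%: scored rate 0.20 × 0.7 = 14%; lost 8.6 × 0.3 = 2.58.

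Letting p also vary from 10% to 30%, the loss runs from 43 × 0.10 × 0.10 = 0.43 to 43 × 0.30 × 0.30 = 3.87 responders.

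**Step 4. Compare with sampling error.** Nine responders of 43 is 20.9% (exact 95% CI 10.0-36.0%). Seven of 43 is 16.3% (6.8-30.7%). The shift lies well inside either interval.

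**The case against.** The best defence is that the notes are loose drafting and that the sensible meaning is patients whose disease is solely non-measurable. That is the only reading under which CR item 1, PR item 2 and the assessment rule all keep a purpose, and the attachment says its summary table, which has no bar, sets out the criteria used in the study. On this view the endpoint is scored correctly and only the wording needs tidying. It is also an untested secondary estimate, with a wide interval and no decision attached.

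Much of this stands. The intended meaning is probably the narrow one, and the consequence is modest. But the text does not settle it. Section 6.9 and Attachment 3 already limit response evaluability to patients with measurable disease at baseline, apart from early progression or death. Within that set the narrow reading leaves the notes almost nothing to do, which pushes a careful reader toward the literal one. Section 7.2.2 instead evaluates everyone who starts therapy, and there the narrow reading has a purpose. The documents do not say which population governs.

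A reader might go further and infer that a multifocal patient whose lesions all shrink can only be scored stable disease. The documents do not support that. The numbered criteria allow CR or PR in such a patient, and relabelling applies only when there are too many lesions to measure, not to every lesion beyond two.

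**Conclusion.** The contradiction is real and confined to Attachment 3: for a patient with both lesion types, the same scan supports CR/PR under one sentence and stable disease under another. Where the notes are followed, the response rate is biased downward and duration of response omits those patients. Where they are not, there is no bias. What is established is inconsistent scoring with a one-directional risk; a definite downward bias in the reported rate is not.

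The size is unknown. The figure of about 0.9-2.6 responders of 43 rests on an assumed 20% true rate, an assumed 10-30% share with mixed disease, uniform use of the notes, and 43 as the denominator. At those shares, 4.3-12.9 of 43 patients would be capped, if the share is the same among non-responders. That should not be read as the number of responders lost, because most of them would not have responded under the assumed rate.

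PFS6, the stage 1 rule at 18 patients and the final rule at 43 are unaffected. The point is worth correcting because it concerns the scoring rule of a named secondary endpoint.

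**What to change.** Make two edits to Attachment 3.

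1. In the notes under CR and PR, insert 'only' before 'non-measurable disease' and 'at baseline' after it, so that the bar applies solely to patients with no measurable lesion at baseline.
2. Where the definitions relabel unfollowed lesions, add that these lesions count under CR item 1 (they must disappear) and PR item 2 (they must not progress), and that they do not by themselves bar CR or PR. Renaming them 'non-target' is optional.

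The cost is a few words in one attachment, with no new data, no extra imaging and no change to sample size. The edits are best made before responses are read, so that the choice of rule cannot be influenced by the results.

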#### CONFIDENTIAL

1. Greater than or equal to 50% decrease compared to baseline in the sum of products of perpendicular diameters of all measurable enhancing lesions sustained for at least 4 weeks. In the absence of a confirming scan 4 weeks later, this scan will be considered only stable disease.
2. No progression of non-measurable disease.
3. No new lesions.\*
4. All measurable and non-measurable lesions must be assessed using the same techniques as baseline.
5. Participants must be on no steroids or must not be on increased doses of steroids within 2 weeks of assessment relative to the dose taken at the time of the previous assessment
6. Stable or improved non-enhancing (T2/FLAIR) lesions on same or lower dose of corticosteroids compared to baseline scan.
7. Stable or improved, for clinical signs and symptoms present at baseline and recorded to be disease related clinically.

*Participants with non-measurable disease cannot have a partial response. The best response possible is stable disease.*

*\*See immunotherapy considerations below regarding new lesions*

Progressive disease (PD). Any of the following criterion must be met:

1. 25% increase in sum of the products of perpendicular diameters of enhancing lesions (over best response or baseline if no decrease) on stable or increasing doses of corticosteroids
2. Patients who decrease corticosteroid use within 2 weeks of MRI assessment relative to the dose taken at the time of the previous assessment cannot be classified as having progressive disease and should be classified as non-evaluable.
3. Any new enhancing measurable lesion\*
4. Clear clinical deterioration not attributable to other causes apart from the tumor (e.g. seizures, medication side effects, complications of therapy, cerebrovascular events, infection, etc.). The definition of clinical deterioration is left to the discretion of the investigator but it is recommended that a decline in the Karnofsky Performance Score (KPS) from 100 or 90 to 70 or less, a decline in KPS of at least 20 from 80 or less, or a decline in KPS from any baseline to 50 or less, for at least 7 days, be considered neurologic deterioration, unless attributable to co-morbid events or changes in corticosteroid dose.
5. Failure to return for evaluation due to death or deteriorating condition

*\*See immunotherapy considerations below regarding new lesions*

Stable disease (SD). All of the following criteria must be met:

1. Does not qualify for CR, PR, or progression.
2. All measurable and non-measurable sites must be assessed using the same techniques as baseline.
3. Stable clinically.

Unknown response status. Progressive disease has not been documented and one or more measurable or non-measurable lesions have not been assessed.

#### Special Considerations for Immunotherapies.

Appearance of new lesions is a criterion that defines progression of disease by RANO criteria. However, transient appearance of new enhancing lesions at either local or distant sites might occur in patients with neuro-oncological malignancies receiving immunotherapy. In such situations, careful radiological and clinical assessments are warranted. In some cases, new enhancing lesions might represent immune responses directed against infiltrative brain tumor cells. In addition, Immune-related response criteria guidelines for non-brain tumor cancers state that early increases in lesion size or new lesions do not

CONFIDENTIAL

define progressive disease unless further progressive changes are confirmed upon follow-up imaging, provided that patients do not have a clinical decline. Therefore, confirmation to define progressive disease is an important, novel aspect of immune-related response criteria. Additionally, the converse argument, the need of follow-up imaging to confirm a radiographic response, has been an accepted component of most response assessment metrics including RANO.

Confirmation of radiographic progression to define progressive disease in iRANO:

- iRANO recommends confirmation of disease progression on follow-up imaging **3 months after initial radiographic progression** if there is no new or substantially worsened neurological deficits that are not due to comorbid events or concurrent medication, and it is 6 months or less from starting immunotherapy.
- Imaging within the 3-month follow-up can be done as medically appropriate at the discretion of the treating clinician.
- The appearance of new lesions 6 months or less from the initiation of immunotherapy alone does not define progressive disease.
- If follow-up imaging confirms disease progression, the date of actual progression should be back-dated to the date of initial radiographic progression.

Note on continuation of therapy pending confirmation of radiographic disease progression: **iRANO** recommends confirmation of disease progression on **follow-up imaging 3 months after initial radiographic progression** if there is no new or substantially worsened neurological deficits that are not due to comorbid events or concurrent medication, and it is 6 months or less from starting immunotherapy (see **Attachment 3** for **iRANO** criteria details). A decision of whether a patient should continue immunotherapy pending confirmation of radiographic disease progression should be established based on perceived benefits and risks. Continuation of immunotherapy may be considered pending follow-up imaging as long as subjects are deriving apparent clinical benefit with minimal and acceptable toxic effects.

By contrast, investigators may consider interrupting immunotherapy for subjects who need a substantial increase in corticosteroids (i.e., >4 mg of dexamethasone or equivalent per day) for evolving symptoms associated with brain edema or who have more than mild treatment-related toxic effects such as at least grade 2 irAEs. These guidelines are included to limit the likelihood of progressive immunotherapy-induced inflammatory changes leading to substantial deficits in otherwise stable or symptom-free patients. In such subjects, an interruption of immunotherapy dosing might be considered pending follow-up imaging.

Furthermore, investigators may discontinue or interrupt immunotherapy at any time if this option seems to be in the best medical interest of the subjects. As a general guidance, resumption of immunotherapy might be taken into account when systemic dexamethasone is decreased to 4 mg/day or less and the contrast-enhancing tumor burden is classified as stable disease, partial response, or complete response on a follow-up scan, or when relevant treatment-related toxic effects have resolved to grade 1 or less or pre-treatment baseline.

The iRANO Response Criteria to be used in this study are summarized in the Table below.

CONFIDENTIAL

### Summary of iRANO Response Criteria

Complete response	Disappearance of all enhancing disease for $\geq 4$ weeks; no new lesions; stable or improved T2/FLAIR; no more than physiological steroids; clinically stable or improved
Partial response	$\geq 50\%$ decrease in the sum of biperpendicular diameters of enhancing disease for $\geq 4$ weeks; no new lesions; stable or improved T2/FLAIR; stable or decreased steroid dose; clinically stable or improved
Minor response	NA
Stable disease	Does not qualify for complete response, partial response, or progressive disease; no new lesions; stable or improved T2/FLAIR; stable or decreased steroid dose; clinically stable or improved
Progressive disease	$\geq 25\%$ decrease in the sum of biperpendicular diameters of enhancing disease; or new lesions; or substantial worsened T2/FLAIR; or substantial clinical decline

[figure not shown]
**Note:** iRANO recommends confirmation of disease progression on follow-up imaging 3 months after initial radiographic progression if there is no new or substantially worsened neurological deficits that are not due to comorbid events or concurrent medication, and it is 6 months or less from starting immunotherapy. If follow-up imaging confirms disease progression, the date of actual progression should be back-dated to the date of initial radiographic progression. The appearance of new lesions 6 months or less from the initiation of immunotherapy alone does not define progressive disease. FLAIR=fluid-attenuated inversion recovery.

**Note:** Typographical error in the Progressive Disease definition, the correct criteria should be "increase" rather than "decrease".

CONFIDENTIAL

This material is the property of the NYU School of Medicine and Langone Medical Center. Do not disclose or use except as authorized in writing by the study sponsor

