### Treatment Planning/Target Volumes

A GTV will be defined using the CT and MRI images.

The GTV includes the post-operative resection cavity if no residual enhancing or non-enhancing tumor is noted. The GTV also includes any non-enhancing tumor as identified on T2/FLAIR. T2/FLAIR signal consistent with edema is not included in the GTV. Therefore a distinction is made between T2 edema (typically without mass effect, sparing the cortical ribbon, obeying the grey/white junction, etc.) with T2 tumor (mass effect with sulcal effacement, involvement of the grey/white junction, obliteration of the cortical ribbon). Care is made to not include any enhancement or T2 signal on the post-operative scan that is due to post-surgical infarct. Fusion of the pre-operative MRI to determine initial extent of the tumor is helpful.

A PTV expansion that is justified based on image guidance and immobilization will be applied. Regardless of immobilization and localization methods, the PTV expansion should be no larger than 3 mm. Therefore, for stereotactic treatment, the PTV is typically 1 mm. For non-stereotactic treatment with IGRT, then the PTV is typically 3 mm.

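### Attachment 3 defines progression twice, and the two versions disagree on T2/FLAIR worsening and on steroid reduction, so a week-24 PFS6 result can depend on which one is used

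*Combined protocol and SAP*

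**What the plan says.** PFS6 by iRANO is the primary efficacy endpoint (Section 3.2). Section 7.2.2 sets six months at six 28-day cycles. Scans are done before Cycle 3 Day 1 and then every 8 weeks (Section 6.6), and the plan describes local reading only.

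Attachment 3 gives the response categories twice.

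- **The list (Response/Progression Categories).** Meeting any one of five items is meant to give PD. Item 1 is a "25% increase in sum of the products of perpendicular diameters of enhancing lesions" on stable or rising steroids. Item 2 says that patients who lowered steroids within two weeks of the MRI "cannot be classified as having progressive disease and should be classified as non-evaluable". Item 3 is "Any new enhancing measurable lesion". Items 4 and 5 cover clinical deterioration and not returning because of death or decline. SD is residual: "Does not qualify for CR, PR, or progression", same techniques, clinically stable.
- **The table (Summary of iRANO Response Criteria).** PD is growth of enhancing disease, new lesions, "or substantial worsened T2/FLAIR; or substantial clinical decline". SD also requires no new lesions and "stable or improved T2/FLAIR; stable or decreased steroid dose".

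The Anti-Tumor Effect Definitions text sends the reader to the list. The sentence introducing the table sends the reader to the table. The note under the table corrects one typographical error (decrease for increase), which is not part of this point.

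**The concern.** The primary endpoint is a count of patients alive and progression-free at six months, compared with fixed cut-offs of 8 of 18 and 23 of 43. If two readers following the same attachment can classify the same patient differently, that count depends on an unstated choice. Sites could make the choice differently, or it could be made at analysis with the data in view.

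Non-enhancing disease is relevant in this trial. Attachment 6 treats it as target: "The GTV also includes any non-enhancing tumor as identified on T2/FLAIR". No inclusion criterion requires measurable enhancing disease. The list also looks incomplete by its own standard: its CR and PR definitions require stable or improved T2/FLAIR, yet a patient who fails that condition can still be SD.

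**Working it through.** **1. Which scan decides.** 6 × 28 = 168 days = week 24. Scans fall at about weeks 8, 16 and 24, so the third on-study scan settles PFS6.

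**2. The two versions side by side.**

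| Finding at week 24 | List | Table | Does this alone change PFS6? |
|---|---|---|---|
| Substantial T2/FLAIR worsening, enhancement stable, clinically stable | SD | PD | Yes, once confirmed and back-dated |
| Enhancement growth of 25% or more during a steroid reduction | Non-evaluable | PD | Possibly; handling not stated |
| Clinical deterioration during a steroid reduction | Item 4 says PD, item 2 read literally blocks it | PD | Possibly; handling not stated |
| New lesion only | PD only if enhancing and measurable | PD for any new lesion | No: both versions say new lesions alone at six months or less are not PD |
| Rising steroids only | SD | Neither SD nor PD | No |
| Disappearance of disease on a stable steroid dose above physiological | CR allowed | CR not allowed | No; response rate only |

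The CR row arises because the list accepts any dose that has not increased ("Participants must be on no steroids or must not be on increased doses of steroids within 2 weeks of assessment"), while the table allows no more than physiological dosing.

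**3. The non-evaluable scan.** Section 7.1.3 counts patients alive without progression and makes early treatment discontinuation a failure. Section 7.2.2 counts progression or death and censors at last follow-up. Neither says how a patient still on treatment with a non-evaluable week-24 scan is scored.

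**4. Reproducing the design.** With stage 1 of 18 (continue at 8 or more) and success at 23 or more of 43 (Section 7.1.3):

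P(positive | p) = Σ over x = 8 to 18 of Bin(x; 18, p) × P(Bin(25, p) ≥ 23 − x)

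- p = 0.40: 0.0474 (plan: 0.047)
- p = 0.60: 0.8272 (plan: 82.7%)

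Both match.

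**5. Sensitivity.** The discordant share m is an assumption; the documents give none.

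| m | Looser reading, p = 0.40 + m | Stricter reading, p = 0.60 − m |
|---|---|---|
| 0 | 0.047 | 0.827 |
| 1/43 (0.023) | p = 0.423: 0.087 | p = 0.577: 0.739 |
| 5% | p = 0.45: 0.157 | p = 0.55: 0.616 |
| 10% | p = 0.50: 0.362 | p = 0.50: 0.362 |

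At the margin, one discordant patient reverses the decision: 7 versus 8 of 18, or 22 versus 23 of 43.

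**The case against.** **The table may be meant to govern.** Its introductory sentence says that it summarises the criteria to be used. But the list is given the same standing a few paragraphs earlier, and a summary that differs from what it summarises does not settle the matter. The figure and the treatment algorithm in Attachment 3 were not readable in the available text, so guidance there cannot be excluded.

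**The pool of discordant patients is narrow.** This stands. Anyone off treatment before six cycles already fails. A T2/FLAIR-discordant patient must have no clinical decline, and the table's PD is then subject to the recommended three-month confirmation. Sections 5.5.2 and 5.5.3 discourage systemic steroids and prefer bevacizumab for edema, so nothing shows that scans will often fall inside a taper.

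**Stronger readings that the documents do not support.**

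- A reader might infer that the new-lesion wording flips week-24 results. It does not do so alone, because the six-month rule is common to both versions. The difference can affect SD labels and later scans.
- A reader might infer that item 2 stops deaths from counting. Section 7.2.2 makes death a PFS event regardless.
- A reader might infer a large upward bias. The list has explicit triggers that the table does not spell out (performance-status thresholds, not returning), the discordance rate is unknown, and the stricter reading costs power instead.

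**Conclusion.** The inconsistency is real and reaches the primary endpoint through two routes only: T2/FLAIR worsening without enhancement growth or clinical decline, and the steroid-reduction rule combined with silence on non-evaluable scans. The first is a clear success/failure conflict. The second depends on how a non-evaluable scan is scored. The remaining differences affect SD and CR labels, response rate or later scans.

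The size cannot be estimated from the documents. The figures in the working assume that every discordant patient is scored the same way; with mixed practice across sites the shift would be smaller. They show that the decision rule is sensitive to a very small number of patients, not that a given inflation will occur. The stated sample size, cut-offs, alpha and power are correct and need no change.

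**What to change.** 1. Reconcile the list and the table into one set of PD and SD definitions, and state that it governs PFS6 at all sites.
2. Carry the table's T2/FLAIR criterion into the PD list and its T2/FLAIR condition into SD. Restrict it to change judged to be tumour rather than edema or treatment effect, and keep it under the existing three-month confirmation and back-dating. The restriction is needed because Sections 5.2.1.2 and 8.1 treat brain edema as expected after HFRT, and Attachment 6 already separates T2 edema from T2 tumour.
3. Make list item 2 a qualifier of item 1 only, so that clinical deterioration during a steroid reduction still counts as PD.
4. State that a non-evaluable week-24 scan is settled by the next evaluable scan, back-dated if PD is confirmed.
5. Align the new-lesion, SD-steroid and CR-steroid wording for consistency.

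Do not add a PD criterion found in neither version, such as progression of non-measurable disease, which appears only as a condition for PR.

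Cost: rewording Attachment 3 and the response CRF, with no added scheduled scans or patients. PFS6 may come out slightly lower than under the list alone.
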